3.2 Secondary Objectives

Secondary analyses will include

- Treatment difference in length of stay
- Treatment difference in time to first spontaneous void

- Relationship between preoperative post-void residual (PVR) and POUR
- Correlation of baseline IPSS and POUR
- Relationship between duration of surgery and POUR

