4.0 Design

The study is a prospective, double-blind, randomized, placebo-controlled trial. Subjects will be randomized 1:1 to receive either oral tamsulosin 0.4 mg or placebo, taken once each evening, beginning 5 days prior to surgery and continuing through the first postoperative day. The primary endpoint is met when the patient is able to spontaneously empty their bladder post-operatively, or needs to be catheterized with either a straight or indwelling urinary catheter for post-operative urinary retention, whichever occurs first.

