6.5 Postoperative considerations

Post-operative care of study patients will include orders for the MMC Acute Retention Protocol, as follows:

- If patient has not voided after 4 to 6 hours or is uncomfortable, a bladder scan is done.
- Straight catheterization is done if bladder scan volumes are greater than 300 to 500 cc (defer if patient is known to chronically retain high volumes and is not uncomfortable).

All patients with POUR will be treated as deemed necessary by the medical team. Treatment of any patient that has POUR will not be guided or constrained by this study.

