6.6 Follow-up

Patients discharged before full course of study drug is given (two postoperative doses) will be instructed to take study drug at home as outlined on patient instruction card, specifically: Patients discharged on day of surgery will take two doses at home (on day 0 and day 1 postop); patients discharged on day 1 postop will take one dose at home; and patients discharged after day 1 postop will not take any study drug. Patients will be advised to discard remaining study drug.

As part of standard of care, it is routine for nursing staff at MMP NSS to follow up with patients via phone call within 24 hours of discharge. As a part of this call, all study patients will be queried on any issues related to urinary retention. They will also be asked if they have continued their study medication as instructed.

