8.2 Secondary Outcome

Secondary outcome measures to be examined are length of stay, relationship between pre-operative PVR and POUR, correlation of baseline IPSS and POUR, relationship of surgical time to POUR, and time to first spontaneous void.

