10.2 Sample Size and Power Calculations

Tamsulosin is hypothesized to reduce POUR compared to placebo in males. Observational data from our center shows a POUR rate of about 17% in patients similar to those to be included in the trial. We hypothesize that the use of the drug can reduce this rate by 50%. A two group continuity corrected c^2 test with a 0.050 two-sided significance level will have 80% power to detect the difference between a control group proportion of 0.170 and a treatment group proportion of 0.085 (odds ratio of 0.454) when the sample size in each group is 264 and a total sample size of 528.

We anticipate recruiting 264 evaluable patients in each group who took at least one dose of study drug and who also had surgery. Due to expected patient drop-out (from surgery cancellations, patients changing their mind or forgetting to take study drug), we expect to enroll up to 610 patients to achieve this.

In a recent chart review, it was found that 670 potentially eligible male patients (age 50-85 and not on preoperative tamsulosin) were seen at MMP NSS in FY 2014, and 680 were seen in FY 2015. Given this volume of patients undergoing spine surgery at MMC, it seems reasonable to expect we could accrue our target enrollment in three years.

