10.3 Randomization

To evaluate the success of randomization, characteristics of patients in the treatment and control groups will be compared using t-tests or their non-parametric equivalents, as appropriate, for continuous variables and chi-square tests or Fisher's exact tests, as appropriate, for categorical variables. The primary outcome, incidence of POUR, will be compared across groups using chi-square tests. If large baseline imbalances between groups are found, a secondary analysis will be performed using a logistic regression model, with POUR as the outcome variable, treatment group as the predictor of interest, and imbalanced patient characteristics as confounding variables. Secondary objectives examine the relationship between other factors and POUR and will be analyzed similarly. Length of stay and time to first void will be analyzed as continuous variables, using t-tests and linear regression models.

REFERENCES

1. Wu, A.K., A.D. Auerbach, and D.S. Aaronson, *National incidence and outcomes of postoperative urinary retention in the Surgical Care Improvement Project*. Am J Surg, 2012. **204**(2): p. 167-71.
2. Baldini, G., et al., *Postoperative urinary retention: anesthetic and perioperative considerations*. Anesthesiology, 2009. **110**(5): p. 1139-57.
3. Boulis, N.M., et al., *Urinary retention following routine neurosurgical spine procedures*. Surg Neurol, 2001. **55**(1): p. 23-7; discussion 27-8.
4. Jung, H.J., et al., *Postoperative urinary retention following anterior cervical spine surgery for degenerative cervical disc diseases*. Clin Orthop Surg, 2013. **5**(2): p. 134-7.

5. Gandhi, S.D., et al., *Patient and surgical factors associated with postoperative urinary retention after lumbar spine surgery*. Spine (Phila Pa 1976), 2014. **39**(22): p. 1905-9.
6. Burger, D.H., et al., *Prevention of urinary retention after general surgery: a controlled trial of carbachol/diazepam versus alfuzosine*. J Am Coll Surg, 1997. **185**(3): p. 234-6.
7. Hooton, T.M., et al., *Diagnosis, prevention, and treatment of catheter-associated urinary tract infection in adults: 2009 International Clinical Practice Guidelines from the Infectious Diseases Society of America*. Clin Infect Dis, 2010. **50**(5): p. 625-63.
8. Scott, R.D. *The Direct Medical Costs of Healthcare-Associated Infections in U.S. Hospitals and the Benefits of Prevention*. 2009 [cited 2015 November 24, 2015].

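### The planned t-test and regression for time to first spontaneous void drop any man with no recorded void; such men are likeliest among those catheterized for retention, expected at 2:1 between arms

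*Combined protocol and SAP*

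**What the plan says.** Section 3.2 lists "Treatment difference in time to first spontaneous void" as a secondary objective, and Section 8.2 repeats the outcome ("relationship of surgical time to POUR, and time to first spontaneous void"). Its whole analysis is one sentence in Section 10.3: "Length of stay and time to first void will be analyzed as continuous variables, using t-tests and linear regression models".

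No section gives a time origin for this outcome, a rule for a man with no recorded void, or a statement on whether a void after catheterization counts as his first spontaneous void.

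Four other sections bear on the point:
- Section 4.0, describing when the primary endpoint is met, sets spontaneous emptying against the alternative that the patient "or needs to be catheterized with either a straight or indwelling urinary catheter for post-operative urinary retention, whichever occurs first".
- Section 6.5 says of men with retention: "Treatment of any patient that has POUR will not be guided or constrained by this study".
- Section 10.1 names need for catheterization among the postoperative data. It does not name void time, but it refers to an attached data sheet that is not among the documents available here.
- Section 10.2 powers the trial to detect "the difference between a control group proportion of 0.170 and a treatment group proportion of 0.085", with 264 men per group.

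**The concern.** A t-test or linear model needs an observed time for every man and silently omits those without one. That matters little if omissions are few and unrelated to treatment. Here the men at greatest risk of omission are those who had the primary outcome, and the trial is designed on the expectation that tamsulosin halves that outcome. The men left in each arm would then be selected by a consequence of treatment, with more of the slow or non-voiding men removed from placebo than from tamsulosin.

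At stake is the interpretation of one between-arm secondary outcome. Its estimate would depend on how many voids after catheterization happen to be written down, and the plan does not control that. Where a later void is recorded, its time also reflects how the catheter was managed, which the study leaves to the clinical team.

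**Working it through.** **1. The plan's own figure.** Inputs from Section 10.2: 0.170 v 0.085, two-sided alpha 0.05, 80% power, continuity-corrected chi-square. Mean proportion = 0.1275.

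Uncorrected n = [1.960 × √(2 × 0.1275 × 0.8725) + 0.842 × √(0.17 × 0.83 + 0.085 × 0.915)]² / 0.085² = 240.5, so 241.

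Corrected n = (240.5/4) × [1 + √(1 + 4/(240.5 × 0.085))]² = 263.5, so 264 per group. The plan's figure is reproduced.

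**2. Men at risk of having no void time.** Expected men with retention: 0.170 × 264 = 44.9 on placebo and 0.085 × 264 = 22.4 on tamsulosin. This is an upper bound on men lost for this reason, because a catheterized man may void later and be timed. If the same share lacks a time in each arm, the losses stay at 2:1:

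| Share of these men with no recorded void | Lost, placebo v tamsulosin | Analysed |
|---|---|---|
| 25% | 11 v 6 | 253 v 258 |
| 50% | 22 v 11 | 242 v 253 |
| 100% | 45 v 22 | 219 v 242 |

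Only steps 1 and 2 use the documents' figures alone. The documents give no void times, so step 3 is illustration.

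**3. Effect on the comparison, under assumed void times.** Both arms have 83% ordinary voiders: log-normal, median 3 h, log-SD 0.5, truncated at 6 h, which gives a mean of 3 × exp(0.125) × 0.812/0.917 = 3.01 h. On placebo 17% are catheterized. On tamsulosin 8.5% are catheterized and 8.5% are spared. Voids after catheterization fall uniformly at 8–16 h (mean 12 h), and a fraction r of them is recorded, at random. With mean void time s in spared men, the t-test compares

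- placebo: (0.83 × 3.01 + 0.17r × 12)/(0.83 + 0.17r)
- tamsulosin: (0.83 × 3.01 + 0.085s + 0.085r × 12)/(0.915 + 0.085r)

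*Case 1: the drug only spares men catheterization, and spared men void at 4–6 h (s = 5).* The percentages come from 4,000 simulated trials of 264 per arm, two-sided 0.05.

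| Later voids recorded (r) | Mean difference, tamsulosin − placebo | t-test: tamsulosin significantly faster | t-test: tamsulosin significantly slower |
|---|---|---|---|
| 100% | −0.60 h | 54% | 0% |
| 75% | −0.44 h | 37% | 0% |
| 50% | −0.26 h | 19% | 0.1% |
| 25% | −0.05 h | 4% | 1.6% |
| 0% | +0.18 h | 0.1% | 36% |

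Gray's test for first void, with catheterization as the competing event, favours tamsulosin in 34% of trials and is never significant in the wrong direction, whatever r is.

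*Case 2: spared men void at 2–4 h (s = 3).* The t-test favours tamsulosin in 78% (all recorded), 47% (half) and 3% (none; mean difference 0.00 h, no reversal). Gray's test does so in 72%.

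*Some drug effect in ordinary voiders (case 1, no later void recorded).* A 5% shortening of their times cuts wrong-direction results from 36% to 6%. A 7% shortening cuts them to about 2%, the level expected by chance.

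*Uniform shift of all times (log-normal, log-SD 0.5 to 0.8, catheterization at 6 h, 17% v 8.5%).* The t-test is right in 98–99% (all recorded), 96–98% (half) and 94–95% (none). In the last case it keeps only 41–51% of the true mean difference. Gray's test is right in 99%.

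**The case against.** The strongest reply is that the documents do not show that any void time will be missing. The outcome's name points to the actual first spontaneous void, whenever it occurs. A man who is straight-catheterized can void later and be timed. Section 10.1 provides for prospective collection at the bedside and by chart review. With every later void recorded, the planned t-test had the right direction in every case examined and was more powerful than Gray's test in cases 1 and 2 (54% v 34%; 78% v 72%). This stands, and it limits the size of the point.

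A second reply is that the competing-event analysis overlaps with the primary outcome. In cases 1 and 2 the arms differ only because fewer men are catheterized. A chi-square test on catheterization detected that in 80–82% of re-run trials, against 38% and 72% for Gray's test. This also stands. Censoring at catheterization under stated assumptions, or a worst-rank test, would be other ways to keep all men, so Gray's test is a reasonable choice and not the only valid one.

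A reader might infer four stronger things that the documents do not support:
- That 45 v 22 men will be missing. This is the expected number with retention; the number without a void time is unknown.
- That the analysis would show tamsulosin to be slower. That needs nearly all later voids missing, almost no drug effect in ordinary voiders, and spared men who void late, all together.
- That Section 4.0 already makes catheterization a competing event here. Its wording describes the primary endpoint and does not define this outcome.
- That first voids are lost through early discharge. Section 6.6 allows for it ("Patients discharged on day of surgery will take two doses at home") and describes a call in which "all study patients will be queried on any issues related to urinary retention", without naming void times. But it does not say that men leave before voiding, and Section 6.5 calls for a bladder scan if a man has not voided after 4 to 6 hours.

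What the replies do not answer is that Section 10.3 commits to methods that drop men without a time and has no rule for them.

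**Conclusion.** The point holds as a minor improvement to one secondary outcome for which the plan states no power. The 2:1 expectation and the upper bound of about 45 v 22 of 264 follow from the plan's own rates; the 2:1 ratio among men actually lost also assumes an equal unrecorded share in each arm. How many void times are lost cannot be judged without the data sheet. The sizes in hours and power rest on assumed distributions. Under them the usual consequence of incomplete recording is attenuation and lost power: with half of later voids recorded, the t-test finds the effect in 19% (case 1) and 47% (case 2) of trials, against 34% and 72% for Gray's test. Under a uniform shift the loss of power is small. With complete recording the t-test is sound in direction. The primary chi-square comparison and N = 528 are not affected.

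**What to change.** In Section 10.3, remove time to first spontaneous void from the t-test sentence and specify:

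1. One stated time origin for all men, for example end of surgery.
2. A time-to-event analysis in all evaluable men: cumulative incidence of first spontaneous void by arm, with catheterization for retention before first void as the competing event, compared by Gray's test.
3. Censoring at last recorded observation for men with neither event.
4. The difference in actual first-void time reported alongside, with the number missing by arm, so that readers can see how far recording was complete.

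Confirm that the data sheet captures the date and time of first void and of catheterization.

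The cost is a few lines of SAP text, plus date-time fields only if the sheet lacks them. There are three downsides: the main effect is no longer a simple difference in hours; it partly overlaps with the primary outcome; and it can have less power than the t-test if every later void is recorded. A separate sensitivity analysis for men who leave the operating room with a catheter is more than this point requires. No change to the primary analysis or sample size is needed.
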